Before Covid-19 children in Greater Manchester were already experiencing waiting times of up to 12 months for dental treatment under GA, often leading to episodes of pain, time off school and repeat courses of antibiotics. According to the Commissioners within GM as of December 2021, there were 1779 children on the waiting list, 716 of whom have been waiting over 52 weeks. These figures show the continued pressure on the system with children waiting an unacceptably long time for treatment. These numbers are now decreasing with the implementation of CFDP, where this pathway is able to take new patients entering the referral system. The CFDPs have shown promising preliminary results with 50% of children seen within a CFDP. The dental commissioning team in GM are committed to increasing the number of CFDPs by reallocating existing funding. There is considerable interest in this type of scheme from other areas of the country in view of the national policy drivers supporting flexible commissioning; following the work in GM further regional pilots have been established this year (for a minimum of 6 months) in the South East of England lead by [name] (who has agreed to join our steering committee if the study is funded – further information is available in the letter of support from [name]). There has also been interest in our research proposal from Northern Ireland and Wales.

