While the pilot indicated promising results, with 50% of children being able to be seen within a CFDP, the long term impacts and health outcomes of the use of CFDP are unknown. There have also been concerns raised from some within the field that children treated within a CFDP may still require future intervention in a more specialist service, within a short period of time. If so, there would not be a reduction on the pressure seen on these services and the overall costs of this scheme would be higher than usual care. The proposed research is required to provide a robust, longitudinal evaluation of the CFDP pathway, building on the initial work from the pilots, which can strengthen the case for nationwide adoption if shown to be successful. Following a realist evaluation approach will also mean the research will provide evidence of what works, for whom and when. The project will provide evidence of long term outcomes (treatment required, pain, use of antibiotics) and a health economic evaluation which can be utilised by commissioners for future schemes. If a high proportion of children referred to specialist services can be treated at CFDPs, this model has the potential to improve access to care across the system. In particular, increased use of CFDPs could allow hospital/specialist services to focus on those in greater need. The implementation of an alternative pathway could allow those urgent cases, and cases for which a dental GA is unavoidable, such as medically compromised children and those with additional needs, to be seen sooner. It may also reduce the need for GA for some children if they are seen sooner than they would otherwise be seen along a traditional pathway.

Research objectives.

The aim of this research is to determine the performance of CFDP pathway compared to a traditional Specialist Paediatric Dental pathway on the longer term oral health and treatment outcomes for children referred to specialist care due to severe decay and the associated health economic costs.

Our primary and secondary research questions (and subsequent objectives/methods) are as follows:

Primary

- *Does treatment through a CFDP reduce treatment under General Anaesthetic when compared to the traditional pathway over a period of 2 years?*
 - Using GA data gained from Hospital Episode Statistics (HES)/Community Dental Service (CDS) records the team will assess the number of GAs carried out along each pathway for dental extraction.

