A referring dentist should chart all teeth in a referral indicating all teeth that are carious and which are symptomatic. When deciding triage outcome, if one or two teeth only are symptomatic (i.e., causing pain) and this could be managed by extraction/restoration, then the child would be suitable for management within CFDP. The child should attend the referring dentist for completion of treatment (shared care model).

Not suitable for management in CFDP:

Child who has developmental defects of permanent teeth requiring treatment

Child with three or more symptomatic carious teeth

Child with unrestorable teeth in three or four quadrants e.g., extractions indicated in three or four quadrants

Child who needs root canal treatment (RCT) in permanent teeth

Child with moderate to severe medical complexities

Child with moderate to severe behavioural complexities

VII. STUDY DESIGN Prospective, comparative, observational cohort study

VI: Planned interventions:

The exposed cohort will receive care following triage and treatment through the alternative pathway (treatment through the new CFDP).

The control cohort (non-exposed) will receive care following triage and treatment through the traditional pathway (treatment through the Specialist Paediatric Dental pathway).

Time scale (see appendix for more detailed time line)

Year 1 – 2023

Months Feb-March -Study set up

Months Feb-March -Ethics application

Months March – PPI development,

Months May -December (2024) – Recruitment

Months May - December (2024) – Data collection (CRF)

Months May – September – Observational data collection

Months May – March (2024) -text message survey

Months Nov – Dec – Data coding

Months August to October – Qualitative interviews

Year 2 – 2024

Months Jan -Feb – NHS BSA application

Months May-July – Text message survey

Months May – September – Observational data collection

Months August to October – Qualitative interviews

Months November to December -Qualitative analysis

Year 3 – 2025

Months March – April finalise NHS application

Months May – August -text message survey

Month June – August – NHS data retrieval (NHS BSA, CDS, clinical records, NHS digital, HES)

Month September – November – Data analysis

Month November -Jan – report write up

Year 3 – 2026

Month Jan – March -Dissemination

Outcomes

Proposed outcome measures

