Primary: The primary outcome, measures whether a child has had a dental extraction under General Anaesthetic two years after referral as indicated in electronic patient records (recorded through HES data or through CDS patient records).

Secondary: The secondary outcomes to be considered in this project include:

- Waiting time until first appointment
- Number of sessions of treatment
- Whether a child was successfully seen and treated. For this outcome success is defined as treatment completed by a dentist that results in a child being referred back to their own dentist or discharged, pain free.
- The number of extractions and restorations as reported in NHS BSA data
- The courses of antibiotics taken during wait and treatment
- Participants referred back into the specialist pathway within two years of referral.
- Dental pain experienced by a child
- Participants views of their treatment and engagement with the dental profession (follow up of dental appointment) as indicated by the responses to the text message. Questions will include an adapted version of the NHS Friends and Family Test, questions on satisfaction, possible negative/adverse experiences, possible positive experiences, and an option for free text comments at the end of the survey.

Qualitative work will focus on two groups: (a) dental professionals (incl. triage, in-practice dental teams, CDS teams and referring practices) and (b) patients (incl. parents and children) accessing and using CFDPs.

(a) Dental teams' attitudes and beliefs regarding CFDP will be examined to better understand what worked well, what created barriers and look at how best to support implementation for such initiatives if they become routine practice.

In a qualitative approach, we will explore dental team beliefs, attitudes, and opinions regarding CFDPs and traditional pathways. To allow for the realist evaluation to take place, a combination of focus groups and one-to-one interviews will take place with the triage team and staff at CFDPs.

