Summary descriptive data will be reported by study arm and overall using tables of frequencies or means and standard deviations as appropriate to characterise the population and identify any imbalance between groups. The comparison of outcomes from the traditional specialist dental service route (control) compared to the intervention treatment under the alternative Child-Friendly Dental Practice will be assessed to determine if there are clinically meaningful and statistically significant differences in key outcomes. The primary outcome is receipt of GA for tooth extraction within two years of initial referral. Referral along both pathways may still result in the need for a GA for some children but a key metric will be to determine whether there

is a meaningful difference in the number of GAs per referral pathway. The primary outcome will be analysed using a mixed effects logistic regression model, accounting for the traditional specialist dental service route or alternative Child-Friendly Dental Practice, with random effects for centre. An adjusted logistic regression analysis additionally accounting for the age, deprivation, ethnicity, sex of the child along with the number of teeth requiring treatment at initial examination (through the CFDP or CDS) will also be undertaken. The analysis dataset will include all participants for whom there is follow-up data from the NHS BSA and the baseline covariates.

Analysis of secondary outcomes will be undertaken in a similar manner using covariate adjusted linear or logistic regression models as appropriate, we will include the modifying effect of deprivation

The health economics analysis will adopt a cost-consequences approach whereby the costs of each pathway will be presented separately but alongside relevant outcomes: 1) dental extractions under GA, 2) count of children who are successfully seen and treated in each pathway, 3) count of treatments performed (extractions, restorations), 4) mean wait time and 5) dental pain experienced by a child. Resource use and costs from the CFDP pathway will also be used in a budget impact analysis. Differences in outcomes will be generated from the quantitative analysis.

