Indicate if following is requested (GA)	GA no GA
Previous dental history	free text
Main reason for referral	tick box
Teeth requested for treatment within referral	dental chart
Complexity score	tick box
Reason for referral	free text
Medical behaviour indicators	tick box
Patient anxiety question	5 questions on likert scale
radiograph included	yes no
Date of referral	date

Text message survey

	Text message Question	Potential response
1	Does your child have any pain in his/her mouth/teeth at the moment? Please reply: yes or no.	"Yes" / "No"
1a	If yes, how would he/she rate this pain from 1 (not too painful) to 10 (most painful pain ever)?	"1-10"
2	Has your child received any antibiotics for a dental problem recently for example, in the last year?	"Yes" / "No" / "Can't remember"
2a	If yes, do you remember how many days he/she was given and for how long did he/she take them? Just type your answer below.	Open text
3	In the last 3 months, has your child had any of the following problems: pain, difficult sleeping, problems eating/drinking?	"pain" / "sleeping" / "eating/drinking"
4	Overall, how was your experience of the service you attended for your child's dental treatment. Please reply: very good, good, neither good nor poor, poor, very poor?	"very good" / "good" / "neither" / "poor" / "very poor"
5	Did you feel the service your child attended for their dental treatment was appropriate for your child? Please reply: yes definitely, yes to some extent, no	"yes definitely" / "yes" / "no"
6	Would you recommend the service to family and friends? Please reply: yes, no, not sure	"Yes" / "No" / "Not sure"

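### The additional adjusted model uses a tooth count made after pathway allocation and the wait, so it may remove part of the pathway effect measured from referral

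*Protocol*

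**What the plan says.** Section X (Data analyses) of the protocol defines the primary outcome as "receipt of GA for tooth extraction within two years of initial referral". It specifies two models:

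- a mixed effects logistic model with pathway and a random effect for centre;
- an additional adjusted logistic model with age, deprivation, ethnicity, sex and the "number of teeth requiring treatment at initial examination (through the CFDP or CDS").

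The same section calls these covariates baseline and limits the analysis set to participants who have them.

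On the order of events, section VI (Planned interventions) says: "The exposed cohort will receive care following triage and treatment through the alternative pathway". The first examination therefore follows allocation. Appendix B records the referral date and the initial appointment date as separate fields on both the CDS and CFDP forms. The Outcomes section lists "Waiting time until first appointment" as a secondary outcome, and the Rationale says of the new pathway: "It may also reduce the need for GA for some children if they are seen sooner".

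Severity is also recorded earlier. The inclusion and exclusion characteristics state: "A referring dentist should chart all teeth in a referral indicating all teeth that are carious and which are symptomatic". They list complete dental charting as an eligibility item. The referral form data in Appendix B include "Teeth requested for treatment within referral", taken from a dental chart.

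**The concern.** A covariate used to control confounding should be fixed before the exposure can act on it. This count is not. Between referral and first examination, a child has been triaged to a pathway and has waited in it. If one pathway sees children sooner and decay progresses in the meantime, part of the difference in tooth counts is produced by the pathway. Holding the count constant then removes that part of the pathway's effect on GA.

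The count is also made by different clinicians in each arm, so differences in how they judge a tooth to need treatment enter the covariate along with true severity.

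Allocation is not randomised, and the first model contains no patient-level covariate. The adjusted model is therefore the one a commissioner would look to for a comparison of like with like.

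**Working it through.** **The plan's own figure.** The Sample size section gives 354 per group for 25% against 15%, 90% power, two-sided 0.05. The pooled two-proportion formula gives n = [1.960·√(2·0.20·0.80) + 1.2816·√(0.25·0.75 + 0.15·0.85)]² / 0.10² ≈ 334.2, so 335. The continuity correction, (n/4)·[1 + √(1 + 4/(n·0.10))]², gives 354. The stated figure is reproduced. It uses no covariate, so nothing below changes it.

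**Order of events.** Referral with charting by the referring dentist (outcome clock starts) → triage to a pathway (exposure) → wait (a secondary outcome) → first CFDP or CDS examination (covariate counted) → GA within two years or not. The covariate comes after exposure and after a variable that the protocol treats as a possible effect of exposure.

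**How much could be removed.** Three inputs are needed: the first-appointment wait in each pathway, the rate at which further teeth come to need treatment, and the effect of each tooth on GA. The protocol gives none of them. Its only wait length, "waiting times of up to 12 months for dental treatment under GA" before Covid-19, concerns treatment under GA and not the first examination. All inputs below are therefore assumptions.

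Let δ be the difference in mean count caused by the wait: δ = (new teeth per year) × (CDS wait − CFDP wait)/12. Let b be the log odds of GA per tooth and d the pathway's direct effect in absolute log odds. On the log-odds scale, approximately:

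share removed = bδ / (d + bδ)

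Take b = 0.3, and d = 0.45 for waits of 12 and 3 months or 0.50 for waits of 6 and 2 months. A simulation of 1,000,000 children per scenario, with CDS GA risk set to 25%, compared adjustment for teeth at referral with adjustment for teeth at first examination.

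| Waits CDS / CFDP (months) | New teeth per year | bδ | Share by formula | OR adjusted for referral count | OR adjusted for first-examination count | Share in simulation |
|---|---|---|---|---|---|---|
| 12 / 3 | 0 | 0 | 0% | 0.64 | 0.64 | 0% |
| 12 / 3 | 0.5 | 0.3 × 0.375 = 0.1125 | 0.1125/0.5625 = 20% | 0.57 | 0.64 | 21% |
| 12 / 3 | 1 | 0.3 × 0.75 = 0.225 | 0.225/0.675 = 33% | 0.51 | 0.64 | 35% |
| 12 / 3 | 2 | 0.3 × 1.5 = 0.45 | 0.45/0.90 = 50% | 0.40 | 0.64 | 51% |
| 6 / 2 | 1 | 0.3 × 0.333 = 0.10 | 0.10/0.60 = 17% | 0.55 | 0.61 | 17% |

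In the 12 / 3 rows, the model adjusted for the first-examination count returns the direct effect (0.64) whatever happens during the wait.

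**Why dropping severity is not the answer.** In one further run (12 / 3 months, 1 new tooth per year), CDS children started with 0.5 more teeth on average. The OR was 0.45 with no adjustment, 0.50 adjusted for the referral count and 0.64 adjusted for the first-examination count. Omitting severity overstates the benefit here. Using the later count understates it.

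The simulation assumes error-free counts, no centre effects, and that the whole effect of waiting passes through the count.

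**The case against.** Four points can be made for the plan.

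1. *The first model does not use the count.* This stands, and it limits the point to the additional adjusted model. A reader might infer that the whole primary analysis is compromised; the protocol does not support that. But the first model adjusts for no patient characteristic, so it cannot stand in for the adjusted one.

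2. *Disease burden at the start of treatment is a legitimate confounder.* The primary research question is worded around treatment through a CFDP, and consented children are recruited when they attend or by letter afterwards, so for many the first examination is close to study entry. This has force: the count does carry information on initial severity. But the outcome is defined from referral in both the Outcomes section and section X, and for that effect the count is post-exposure. The adjusted estimate is off target only if the total effect from referral is what is wanted.

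3. *The protocol does not say that waiting acts through the number of teeth.* Correct. The Rationale says only that earlier care may reduce GA for some children. Worsening of teeth already decayed, pain or anxiety need not change a count. A reader might infer that adjustment blocks the whole benefit of being seen sooner. Only the part acting through the count is removed.

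4. *A waiting-time difference is not stated.* Also correct. Waiting time is an outcome to be measured, and no expected value by pathway is given. The effect is conditional on such a difference.

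**Conclusion.** The point holds for the additional adjusted model. Its severity covariate is described as baseline but is measured after pathway allocation and the wait, by different clinicians in each arm, while the outcome runs from referral. If waits differ and teeth deteriorate meanwhile, the adjusted odds ratio is not the total pathway effect from referral. If the CFDP is the faster pathway, the shift from this route is toward no effect.

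The size cannot be derived from the protocol. The illustrations run from 0% to about half of the log odds ratio and rest wholly on assumed waits, decay rates and per-tooth odds. A reader might infer that a quarter to a half of the planned 25% to 15% effect would be lost. That needs a long wait difference and steady new decay, neither of which the protocol gives, and any fair range includes zero.

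A reader might also infer that many unexamined children drop out because they lack the count. Consented children are recruited on or after attending, and the CFDP numbers in the Sample size section are patients seen and treated. The loss would mainly concern the unconsented cohort from the referral management system, and its extent is not shown.

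**What to change.** In the adjusted model, replace the first-examination count with one count from the referral form's dental chart, named before analysis. The number of teeth requested for treatment within the referral is one candidate. Carious, symptomatic and requested teeth measure different things, so the choice must be fixed and not left open. The referral chart pre-dates allocation, comes from referring dentists in both arms, does not depend on attendance, and complete charting is already an eligibility item.

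Report the first-examination count descriptively by pathway. If it is also wanted in a model, add a sensitivity analysis labelled as not estimating the total effect from referral.

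The cost is one covariate changed in section X, with data already listed for collection and no change to the sample size. The downside is that referral charting may be less precise than the pathway examination and may leave some residual confounding by severity; the report should say so.

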Patient_charge_due	Patient charge due (££) for ever CoT
Patient_charge_collected	Patient charge actually collected (i.e. if they did not complete the course of treatment - are there outstanding payments owed? = remittance)
TX_COMPLETE	Is the treatment complete or incomplete? NO=0, Y=1
TX_DAYS	Interval in days between date of acceptance and date of completion or last visit
YEAR_MONTH	Date of when the form was submitted
TREATMENT_DATE	date of treatment
TREATMENT_CHARGE_BAND	treatment charge band
CONTRACT_TYPE	Type of contract (we are requesting information on: GDS / GDS and / PDS - no ortho needed).
12_MONTH_LIST	ND looking into this = Number of unique patients seen in previous 12 months (contract level)
24_MONTH_LIST	ND looking into this - Number of unique patients seen in previous 24 months (contract level)
PRACTICE_LSOA	Lower super output area of dental practice address
PRACTICE_CCG	Clinical commissioning group of dental practice address
PRACTICE_CCG_POPULATION_PER_DENTIST	Population per dentist of practice Clinical Commissioning Group
CONTRACT_UDAs	Annual number of contracted UDAs
CONTRACT_UDA_VAL	UDA Value (price per UDA)
CONTRACT_RADS_PER_100	Radiographs rate per 100 FP17s for contract (unless this is available by performer?)
CONTRACT_REATTEND	Average Re-attendance interval (days) on contract. I.e. number of days between courses of treatment completion and start of new course of treatment
FORM_ID	Is this just each treatment line - if so keep in
FOUNDATION_DENTIST	foundation dentist
AGE_LAST_3103	Dentists age. Age at that CoT (Age at march of that year - preceding treatment)
PERFORMER_NUMBER	NHS BSA to TRANSFORM into another numeric value to allow us to still identify the same performers within the dataset but not linkable to any real-world information
PERFORMER_PROVIDER	Is the performer also a provider (i.e. contract holder)? N=0, Y=1
PERFORMER_DATE_REGISTERED	Date of performer entry to General Dental Council register

PERFORMER_BDS_PLACE	Place of performer BDS qualification (from GDC / NHS Performers list)
PERFORMER_GENDER	
ADV_MAN_SERV	
ADV_MAN_SERV_COUNT1	YES "referral for advanced mandatory service"
ANTIBIOTICS	
ANTIBIOTICS_COUNT	
BEST_PRACTICE_COUNT	
CROWNS	
CROWNS_COUNT	
DECAYED_PERM	This is part of the DMFT index number of decayed teeth.
DECAYED_PERM_COUNT	This is part of the DMFT index if they completed the Decayed component. 0=N and 1=Y
ENDODONTIC_TREATMENT	
ENDODONTIC_TREATMENT_COUNT	
EXEMINATION_COUNT	
EXTRACT_ORTHO_COUNT	

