FILLED_PERM	Number of filled permanent teeth (in DMFT component). This is part of the DMFT index
FILLED_PERM_COUNT	If the Filled component was completed or not. N=0, 1=Y. This is part of the DMFT index
FISSURE_SEALMENTS	
FISSURE_SEALMENTS_COUNT	
FLOURIDE_VARNISH_COUNT	
INLAYS	
INLAYS_COUNT	
MISSING_PERM	Number of missing permanent teeth . This is part of the DMFT index
MISSING_PERM_COUNT	if the M component was completed or not (0=N, 1 =Y). This is part of the DMFT index
RADIOGRAPHS	Number of radiographs taken (will only be from 2015 as not in legacy data)
RADIOGRAPHS_COUNT	If rads were taken or not (N=0, Y=1)
SCALE_POLISH_COUNT	
EXTRACTIONS_COUNT	If extractions were carried out

EXTRACTIONS	How many extractions
PERM_FILL_COUNT	If fillings were carried out. 0=NO, 1-Y
PERM_FILL	Number of permanent fillings and / or sealant restorations provided
RECALL_COUNT	Was a recall interval completed? Y=1, N=0
RECALL_INTERVAL	What is the recall interval? (3,6,12,18,24 months)
LAST_TREATMENT_DATE	This is date of last CoT
NUM_PERFORMERS	Total number of unique performers that the patient has seen over the 10 years. (Will be the same number in each row)
NUM_PRACTICES	Total number of different practice addresses the patient has attended over th 10 years.
DECAYED_deciduous	Decayed deciduous. This is part of the dmft index number of decayed teeth.
DECAYED_deciduous_COUNT	This is part of the dmt index f they completed the Decayed (deciduous) componenent. 0=N and 1=Y
FILLED_deciduous	Number of filled deciduous teeth (in dmft component). Double check this isn't fillings carried out. This is part of the DMFT index
FILLED_deciduous_COUNT	If the Filled (deciduous) component was complet dmfted or not. N=0, 1=Y. This is part of the DMFT index
MISSING_deciduous	Number of missing deciduous teeth . This is part of the dmft index
MISSING_deciduous_COUNT	if the M (deciduous) component was completed or not (0=N, 1 =Y). This is part of the dmft index
Sedation	Sedation
Treatment on referral	Treatment on referral
Further treatment within 2 months –	Further treatment within 2 months –

HES NHS digital CDS data

Link using DOB Name, URN NHS number	PANDA ID	dental GA (yes no)	Date of referral for DGA	Date of dental GA (if occurred)
-------------------------------------------	----------	--------------------	--------------------------	------------------------------------

Referral form data

Patient complaint	free text
-------------------	-----------

Reason for urgent care	free text

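### The analysis set requires NHS BSA follow-up, a source that does not hold the GA outcome, so the primary comparison is at risk of selection bias and avoidable loss of power

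*Protocol*

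**What the plan says.** Section X (Data analyses) defines the primary outcome as GA for tooth extraction within two years of referral. It gives a mixed effects logistic model with random centre effects, then an adjusted model "additionally accounting for the age, deprivation, ethnicity, sex of the child" and for the number of teeth needing treatment at the first examination. The next sentence sets the population: "The analysis dataset will include all participants for whom there is follow-up data from the NHS BSA and the baseline covariates". No separate set is given for the primary outcome.

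Elsewhere the protocol takes GA from other sources:

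- Research objectives: "Using GA data gained from Hospital Episode Statistics (HES)/Community Dental Service (CDS) records".
- Proposed outcome measures: GA is "recorded through HES data or through CDS patient records".
- Appendix B: the field "dental GA (yes no") stands under the HES / NHS Digital / CDS heading. The NHS BSA headings list sedation but no GA item.

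On the scope of the NHS BSA extract, the contract-type row of Appendix B reads "we are requesting information on: GDS / GDS and / PDS". The Background says that the CFDP scheme is funded through variations to GDS contracts. The protocol does not give the CDS contract type or say whether CDS treatment appears in NHS BSA data.

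**The concern.** The rule makes entry to the primary analysis depend on a dataset that the primary outcome does not need. Having NHS BSA follow-up is also not a baseline property. It depends on where a child is treated and whether the child later attends a practice whose activity is in the extract, and both come after referral.

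A CFDP course of treatment should itself create an NHS BSA record. If CDS activity is not in the extract, a CDS child qualifies only through other primary-care attendance, and that may depend on whether the child had a GA. Inclusion could then be related both to the arm and to the outcome, which is the setting for selection bias in the main estimate. Even without bias, each child dropped costs power.

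The condition on baseline covariates has a similar effect. The unadjusted model does not use them. One of them, the number of teeth needing treatment, is recorded at the first CFDP or CDS visit, and both forms allow for no appointment having been made.

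**Working it through.** **1. The plan's own figures.** Inputs from the Sample size section: 25% versus 15%, two-sided 0.05, 90% power.

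n = [1.960·√(2·0.20·0.80) + 1.2816·√(0.25·0.75 + 0.15·0.85)]² / 0.10² = (1.1087 + 0.7193)² / 0.01 ≈ 334.2, so 335 per group.

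With continuity correction: (334.2/4)·[1 + √(1 + 4/(334.2·0.10))]² ≈ 353.9, so 354. The stated 354 is reproduced.

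The revised plan has 292 CDS and 460 CFDP children. The pooled proportion is (292·0.25 + 460·0.15)/752 = 0.1888. Power = Φ[(0.10 − 1.960·0.02928)/0.03032] = Φ(1.405) = 92.0% (90.5% with continuity correction). The 708 is the number needed at the end of the study, and no allowance for non-linkage is stated.

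**2. Effect of the rule.** Let p be the true GA risk in the CDS arm, and let a and b be the shares of CDS children with and without a GA who have NHS BSA follow-up.

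- Observed risk = p·a / [p·a + (1 − p)·b]
- Children retained = 292·[p·a + (1 − p)·b]

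The documents give neither a nor b, so the values below are assumptions. All 460 CFDP children are taken as retained, with true risks of 25% (CDS) and 15% (CFDP). Power is without continuity correction and ignores clustering by centre.

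| a (GA) | b (no GA) | CDS retained | Observed CDS risk | Difference from 15% | Power |
|---|---|---|---|---|---|
| 1.0 | 1.0 | 292 | 25.0% | 10.0 points | 92.0% |
| 0.8 | 0.8 | 234 | 25.0% | 10.0 points | 88.3% |
| 0.6 | 0.6 | 175 | 25.0% | 10.0 points | 81.9% |
| 0.6 | 0.8 | 219 | 20.0% | 5.0 points | 37.8% |
| 0.8 | 0.6 | 190 | 30.8% | 15.8 points | 99.2% |

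For example, with a = 0.6 and b = 0.8: 0.25·0.6 / (0.25·0.6 + 0.75·0.8) = 0.15/0.75 = 20.0%. The high power in the last row belongs to an inflated difference and is no advantage.

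**3. On the odds-ratio scale of the primary model.** Selection multiplies the CDS odds of GA by a/b. The true odds ratio, CFDP to CDS, is (0.15/0.85)/(0.25/0.75) = 0.53. With a/b = 0.75 it becomes 0.176/0.250 = 0.71. With a/b = 1.33 it becomes 0.176/0.444 = 0.40. The odds ratio is distorted only if a/b differs between the arms.

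**4. No true difference.** With 25% in both arms, coverage of 60%/80% (GA/no GA) rejects in about 30% of studies and 80%/60% in about 33%, instead of 5%.

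**The case against.** The strongest reply is that the protocol does not show that any CDS child is lost. PDS contracts are in the extract. The secondary outcome "The number of extractions and restorations as reported in NHS BSA data" carries no arm restriction, so the authors appear to expect NHS BSA data on both pathways. Every eligible child was referred by a general dental professional, and the success outcome includes return to the child's own dentist, so high street records within two years are plausible in both arms. The sentence may also have meant routine follow-up data in general.

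Most of this stands, and it limits the claim. A reader might infer that CDS children are excluded and that the GA comparison is biased in a known direction. The documents do not support that: coverage is not given, bias needs coverage that depends on GA status, and the table shows that the direction can go either way. In both of its unequal-coverage rows the CDS risk stays above the CFDP risk.

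Two further inferences also fail:

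- That the set with complete covariates would be empty because ethnicity is not collected. No ethnicity field is visible in Appendix B, but one CFDP form header is cut off in the available text, and Data handling says that routine sources are not confined to those it names.
- That the cost-consequences table would hide extractions under GA. The Cost effectiveness section adds local clinical records to NHS BSA for dental treatment and takes GA extractions from HES and CDS software as a separate item.

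What the reply does not remove is the rule itself. It names NHS BSA alone, applies to the primary outcome as written, and can discard children whose outcome is known. This is a stated rule that is wrong for its purpose, not a detail left to an analysis plan.

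**Conclusion.** The concern holds as a risk. The analysis set is conditioned on a post-referral source that does not supply the primary outcome, and differential loss by arm is plausible from the contract arrangements described. The size and direction of any bias cannot be derived from the protocol.

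Under the assumed coverage values, a true 10-point difference could appear as anything from 5 to 15.8 points. If coverage does not depend on GA status, the risk is not distorted and the cost is power alone: about 88% at 80% CDS coverage, against 92.0% with all 292 CDS children. These figures assume full CFDP retention, true risks of 25% and 15%, and no clustering. The sample size calculation itself is not in error on this point.

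**What to change.** - **Primary set.** Include all eligible triaged children successfully linked to the HES/CDS outcome sources, with the same sources and linkage rule in both arms, whether or not they have an NHS BSA record. Linked should mean that the child's identifiers were matched and the source searched. Being submitted for tracing is not enough, because failed matches would then be undefined or counted as no GA.
- **NHS BSA condition.** Keep it only for outcomes taken from NHS BSA.
- **Covariates.** Do not let a missing adjustment covariate remove a child from the unadjusted primary model. Confirm where ethnicity comes from.
- **Reporting.** Give HES/CDS and NHS BSA linkage by arm, and NHS BSA linkage also by GA status, so that readers can see whether coverage is related to the outcome.
- **Lesser, separate point.** Reconcile the secondary outcome on extractions and restorations, defined from NHS BSA, with the CFDP and CDS forms, which also count extractions, and with the local clinical records named under Cost effectiveness.

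The cost is a change of wording and slightly more analysis and reporting. If ethnicity turns out to need a new field for the unconsented cohort, that data flow is under Confidentiality Advisory Group approval and may need an amendment. The change should be made before the NHS data are retrieved.
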